8.4 Sample Size and Accrual Rate

8.4.1 Sample Size

For the primary endpoint of ORR, a sample size of 37 response-evaluable subjects will provide power of 77% with 2-sided 5% alpha and 88% with 1-sided 5% alpha to show ORR improvement from H_0 of 5% to H_1 of 20%, under protocol treatment. Based upon a subset with non-measurable disease enrolled to Stages 1 and 2 before amendment requiring RECIST 1.1-measurable tumors for enrollment to Expansion Cohort, along with potential for dropout in this population with comorbidity of biliary obstruction and liver disease, it is estimated that total enrollment of 42 subjects will include at least 37 response-evaluable subjects.

The key secondary endpoint of %PFS6 was previously the primary endpoint for Stages 1 and 2, prior to amendment adding Expansion Cohort, which also changed to primary endpoint of ORR based upon the promising response rate observed in Stages 1 and 2. For the key secondary endpoint of PFS, an expected overall study PFS-evaluable sample size of at least 40 patients will have power 78% with 2-sided alpha 5% and power 87% with 1-sided alpha to show PFS improvement from H_0 of 20% to H_1 of 40% on protocol therapy.

Pre-amendment, a Simon's 2 stage design was employed to determine if adequate efficacy was observed in Stage 1 to warrant proceeding to Stage 2. The pembrolizumab/GM-CSF combination was considered worthy of additional investigation if the true %PFS6 is 50%, and hence the alternative hypothesis, $\%PFS_1=0.50$. Therefore assuming an α error probability of 5%, and a β error of 20%, the first stage had 9 patients. If ≤ 2 of 9 had been observed progression-free, the study would not proceed to second stage. Since ≥ 3 of 9 patients are observed progression-free at 6 months (4/9 achieved PFS6 in Stage 1), enrollment continued to the second stage with 18 additional patients, with a goal of at least 24 evaluable patients (with planned over-enrollment of 3 additional patients to account for expected 10% dropout rate). If ≤ 9 patients are observed progression-free at 6 months out of 24 evaluable patients by the end of second stage, then no further investigation of the drug is warranted under this PFS6 hypothesis. Conversely, if ≥ 10 patients are progression-free at 6 months among Stages 1 and 2 subjects, the study would be considered positive for the hypothesis: H_0 : $\%PFS_0 < 25\%$ versus H_a : $\%PFS_1 > 50\%$.

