8.4.5 Interim Efficacy Analysis

An interim efficacy analysis examined %PFS6 after the first stage (n=9) are evaluable for PFS6. See Section 8.2. Three or more patients ($r_1 \geq 3$) were required to be progression-free at 6 months to continue 2nd stage enrollment. If ≤ 2 patients were progression-free at 6 months in first stage, the study would have been placed on hold and evaluated for closure for lack of efficacy. If the true %PFS is 0.25, the probability of terminating the study during the first stage is 0.60. If the true %PFS is 0.50, the probability that the study will be stopped during the first stage is 0.09. Accrual was continued during interim efficacy analysis. Four of 9 patients enrolled to Stage 1 were determined to be progression-free at 6 months, thus Stage 2 enrollment was continued and completed in September 2017.

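### The Stage 1-2 PFS6 success cut-off of 10 is set for 24 evaluable patients, but 27 were enrolled and Section 8.4.1 gives no boundary for 25 to 27, where the stated 5% error is exceeded

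*Combined protocol and SAP*

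**What the plan says.** Section 8.4.1 describes the two-stage Simon design that sized Stages 1 and 2 when PFS6 was the primary endpoint. It tests 25% against 50% with 5% type I and 20% type II error. If 2 or fewer "of 9 had been observed progression-free, the study would not proceed to second stage". Four of nine met the endpoint, and "enrollment continued to the second stage with 18 additional patients". The same paragraph explains the total: the goal was at least 24 evaluable, with three extra patients for an expected 10% dropout.

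The final decision is then given in two consecutive sentences:

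- Negative: 9 or fewer "patients are observed progression-free at 6 months out of 24 evaluable patients by the end of second stage".
- Positive: at least 10 "patients are progression-free at 6 months among Stages 1 and 2 subjects, the study would be considered positive for the hypothesis".

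The first names 24 evaluable patients. The second names the two stages and gives no number. Section 8.4.5 gives the first-stage operating characteristics: "If the true %PFS is 0.25, the probability of terminating the study during the first stage is 0.60" and "If the true %PFS is 0.50, the probability that the study will be stopped during the first stage is 0.09".

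**The concern.** The two halves should be complements on one denominator, but the wording does not secure that. The target of 24 is a floor, and nothing says what happens if fewer than three patients drop out. With 25 to 27 evaluable, an analyst could keep the cut-off of 10, raise it, or restrict the count to 24, and the text does not choose.

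Other parts of the plan make more than 24 likely:

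- Section 1.0 expects 40 of 42 patients to be evaluable for PFS6. If no more than two are lost in the whole study, at least 27 − 2 = 25 of the Stage 1-2 patients count.
- Section 8.3.2 keeps patients censored without progression in the PFS6 denominator and treats them as not having progressed, so they raise the number counted and can add successes.
- Section 8.5.2 defines evaluability for ORR only. No definition for PFS6 brings the count back to 24.

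What is at stake is a statement that Stages 1 and 2 met their PFS6 hypothesis at the 5% level when the rule applied does not hold that level.

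**Working it through.** **Inputs** (Sections 8.4.1 and 8.4.5): n1 = 9; continue if at least 3 of 9; null p = 0.25; alternative p = 0.50; type I error 5%; type II error 20%; final cut-off r = 10; planned evaluable N = 24; enrolled 9 + 18 = 27. All nine Stage 1 patients are taken as evaluable, so Stage 2 contributes N − 9.

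**Formula.** With X1 ~ Bin(9, p) and X2 ~ Bin(N − 9, p),

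P(positive) = Σ over x = 3 to 9 of P(X1 = x) × P(X2 ≥ r − x).

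**Step 1: reproduce the plan.** P(X1 ≤ 2) is 0.601 at p = 0.25 and 0.090 at p = 0.50, matching the stated 0.60 and 0.09. A full search for the Simon optimal design with these inputs returns 2/9 and 9/24, the plan's boundaries. The dropout allowance also agrees: 24 / 0.9 = 26.7, rounded up to 27.

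**Step 2: type I error of at least 10, term by term, p = 0.25.**

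| x | P(X1 = x) | P(X2 ≥ 10 − x), N = 24 | Product | P(X2 ≥ 10 − x), N = 27 | Product |
|---|---|---|---|---|---|
| 3 | 0.23360 | 0.05662 | 0.01323 | 0.13898 | 0.03247 |
| 4 | 0.11680 | 0.14837 | 0.01733 | 0.28255 | 0.03300 |
| 5 | 0.03893 | 0.31351 | 0.01221 | 0.48133 | 0.01874 |
| 6 | 0.00865 | 0.53871 | 0.00466 | 0.69431 | 0.00601 |
| 7 | 0.00124 | 0.76391 | 0.00094 | 0.86469 | 0.00107 |
| 8 | 0.00010 | 0.91982 | 0.00009 | 0.96054 | 0.00010 |
| 9 | 0.00000 | 0.98664 | 0.00000 | 0.99436 | 0.00000 |
| Sum | | | **0.0485** | | **0.0914** |

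**Step 3: all possible counts from 24 to 27.** Error is at p = 0.25 and power at p = 0.50.

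| Evaluable N | Error, cut-off 10 | Power, cut-off 10 | Error, cut-off 11 | Power, cut-off 11 |
|---|---|---|---|---|
| 24 | 4.85% | 80.5% | 2.0% | 70.5% |
| 25 | 6.1% | 83.6% | 2.7% | 75.5% |
| 26 | 7.6% | 85.8% | 3.6% | 79.6% |
| 27 | 9.1% | 87.4% | 4.6% | 82.7% |

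The cut-off of 10 holds 5% at 24 and at none of 25, 26 or 27.

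**Step 4: the null the plan now uses for PFS6.** At p = 0.20 the same two-stage rule with cut-off 10 has error 1.1% at N = 24 and 2.4% at N = 27. The excess exists only against the 25% null that this rule states.

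**The case against.** The case on the other side has four parts.

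1. *The rule is history.* The paragraph is introduced as pre-amendment, Section 8.1 says the primary endpoint then became ORR, and Section 8.6 plans no test of Stage 1-2 PFS6 against 10. This stands as a limit on the consequences. It does not remove the point, because the current SAP still says when the study would count as positive on this hypothesis, and whether Stages 1 and 2 met their original endpoint is a natural result to report.

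2. *Ten of 24 was meant.* The success sentence is introduced as the converse of the futility sentence, and naming the two stages may only mean that the count is cumulative. This is probably the intent. A reader might infer that the rule is written for every enrolled patient, but the text does not say so, and Section 8.3.2 defines PFS6 over evaluable patients. Even on the favourable reading, nothing is said about 25 to 27.

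3. *The three extra patients were expected to drop out.* If they did, N = 24 and the error is 4.85%. That is correct. The documents never give the number of evaluable Stage 1-2 patients. The 40-of-42 figure is a whole-study expectation, so it makes more than 24 likely without establishing it.

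4. *Raising the bar to 11 has its own costs.* It does: power falls below 80% at 25 and 26. It would also be a new cut-off, since Section 8.4.5 dates the end of Stage 2 enrolment to September 2017. This objection decides which remedy to prefer.

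**Conclusion.** The point holds as an incomplete decision rule. The boundary is right for 24 evaluable patients, its positive half does not carry that denominator, and no boundary covers 25 to 27. Against the 25% null the type I error is 4.85% at 24, 6.1% at 25, 7.6% at 26 and 9.1% at 27, so the stated 5% is exceeded unless at least three of the 27 are non-evaluable. If the plan's expectation of at most two non-evaluable patients overall is met, the range is 6.1% to 9.1%. These figures assume the first-stage rule was applied as written and all nine Stage 1 patients count.

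Three stronger readings go too far:

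- That the rule nearly doubles the error (9.14 / 5 = 1.83 times) is the worst case and needs all 27 to be counted.
- That the Simon design was miscalculated is wrong, since every stated design figure reproduces.
- That the trial's main conclusions are compromised does not follow: the ORR test and the PFS6 test on 40 patients (20% against 40%) do not use this rule.

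**What to change.** In Section 8.4.1, use the same denominator in both halves: 9 or fewer is negative and 10 or more is positive among the first 24 evaluable Stage 1-2 patients in enrolment order. Say what makes a patient evaluable for PFS6. Report PFS6 in all evaluable Stage 1-2 patients as an estimate with its confidence interval. This keeps the original boundary, with error 4.85% and power 80.5%. The cost is a few sentences, and up to three patients fall outside the formal test while still contributing to the estimate.

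If all evaluable patients are to be tested instead, the cut-off must be 11 for 25, 26 or 27 patients (error 2.7%, 3.6% and 4.6%; power 75.5%, 79.6% and 82.7%). The SAP should then disclose that this cut-off was set after Stage 2 enrolment was complete, and that power is below the design's 80% at 25 and 26. The first option is preferable because it introduces no new threshold.

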8.4.2 Accrual Rate

Accrual of approximately 2 patients per month was achieved for Stages 1 and 2, with completion of enrollment to Stages 1 and 2 within 16 months. Owing to additional eligibility requirements for paired biopsies and measurable disease, accrual rate for Expansion Cohort is expected to be slower, approximately 1-1.5 per month with enrollment completion within 12 months.

8.4.3 Interim Analyses

8.4.4 Interim Safety Analysis and Stopping Rules

An interim safety analysis was performed after completion of 1st stage enrollment corresponding to approximately 33% enrollment (9 patients in Safety Cohort). The interim safety analysis examined safety during first 3 cycles of treatment (1 cycle single-agent pembrolizumab followed by 2 induction cycles with GM-CSF for total of 9 weeks). If $>20\%$ or more SAE and/or ECI, and/or $>50\%$ Grade ≥ 3 adverse events by NCI CTCAE v.4.0, have occurred during first 3 cycles of treatment and are assessed as both clinically relevant and at least possibly treatment-related, a decision would have been required whether to amend or close the study after the 1st stage. The interim safety analysis showed overall rate of Grade ≥ 3 at least possibly related AE rate of 11%, with 1 related SAE event (11%), meeting criteria to proceed with enrollment to Stage 2 Efficacy Cohort.

The target rate of $\leq 50\%$ at least possibly treatment-related \geq Grade 3 events during the first 3 cycles was conservative based upon rate of 70% for all-cause Grade 3 or 4 toxicity observed with standard first-line chemotherapy in this population,⁹ and treatment-related Grade 3-5 rate of approximately 45% for the combination of ipilimumab plus GM-CSF in advanced melanoma

patients.³⁴ Accrual was placed on hold after the 9th patient was enrolled during 1st stage safety analysis, until at least 8 of the 9 patients had potential to complete 3 cycles (9 weeks) of treatment or had a qualifying safety event. Accrual resumed after completion of safety interim analysis without unexpected safety signals identified.

8.4.5 Interim Efficacy Analysis

An interim efficacy analysis examined %PFS6 after the first stage (n=9) are evaluable for PFS6. See Section 8.2. Three or more patients ($r_1 \geq 3$) were required to be progression-free at 6 months to continue 2nd stage enrollment. If ≤ 2 patients were progression-free at 6 months in first stage, the study would have been placed on hold and evaluated for closure for lack of efficacy. If the true %PFS is 0.25, the probability of terminating the study during the first stage is 0.60. If the true %PFS is 0.50, the probability that the study will be stopped during the first stage is 0.09. Accrual was continued during interim efficacy analysis. Four of 9 patients enrolled to Stage 1 were determined to be progression-free at 6 months, thus Stage 2 enrollment was continued and completed in September 2017.

8.5 Analysis Populations

8.5.1 Safety Population

The safety population will include all enrolled patients who receive at least one dose each of pembrolizumab plus GM-CSF and have the potential to complete 3 cycles (9 weeks) of safety assessments. All patients will be evaluable for toxicity and safety assessment from the time of their first treatment with the investigational combination. Patients who are determined ineligible after enrollment or who are not evaluable for safety analysis (e.g., due to withdrawal of consent or complications of biliary obstruction or drainage procedures assessed as not related to tumor progression and not treatment-related toxicity) prior to completing 3 cycles (9 weeks) will be replaced (see Section 5.9).

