4.3.5.1 Rationale for Expansion Cohort Schedule and Biopsies

An important exploratory objective of the Expansion Cohort is to obtain paired biopsy samples from patients while on treatment with pembrolizumab monotherapy and in combination with GM-CSF, in addition to archival pre-treatment samples. Correlative analyses of tumor and TIIC PD-L1 expression, TIIC profiles, and PBMC profiles will explore for changes associated with

pembrolizumab alone and with addition of GM-CSF to better understand the differential contributions of each study drug to the observed clinical and radiographic responses in this study.

To enable comparisons of pembrolizumab monotherapy and in combination with GM-CSF, the schedule for the Expansion Cohort will be the same as the Safety Cohort, starting with 1 cycle of pembrolizumab monotherapy before adding induction GM-CSF during Cycles 2 and 3. The observed safety and efficacy of the Safety Cohort and Efficacy Cohort are similar, though limited by small sample sizes, supporting the choice of the Safety Cohort schedule for the Expansion Cohort. Biopsies will be planned during Week 3 of pembrolizumab monotherapy and Week 9 after addition of GM-CSF and after first restaging imaging has been obtained. PMBC profiles will be compared between the Safety and Expansion Cohorts (expected n=23) and the Efficacy Cohort (n=18), enabling further characterization of the impact of GM-CSF on immune cell profiles in a larger group of subjects.

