4.3.6.3 Safety Endpoints

Safety is a key secondary endpoint for this novel combination. The combination of GM-CSF plus ipilimumab showed an improved toxicity profile compared to ipilimumab alone with significantly lower rates of treatment-related grade 3-5 adverse events (44.9% versus 58.3%, p=0.04),³⁴ but the safety of pembrolizumab in combination with induction GM-CSF has not been studied in humans. The interim safety analysis after 9 patients in the Safety Cohort completed 3 cycles of therapy (1 cycle of pembrolizumab followed by 2 cycles with GM-CSF induction plus pembrolizumab, for total of 9 weeks in the Safety Cohort) or been removed for related toxicity events showed acceptable safety to continue enrollment to the Efficacy Cohort (see Section 4.3.5). The interim safety analysis showed that related ≥ Grade 3 toxicity rate during the first 3 cycles did not exceed 50%, a target set based upon the safety profile of standard chemotherapy in biliary tract cancers, and based upon the reported rate of related Grade 3-5 toxicity of approximately 45% for the combination of ipilimumab plus GM-CSF in advanced melanoma.^{9,34} The all-cause Grade 3 or 4 toxicity rate was approximately 70% in advanced biliary cancer patients treated with combination of standard 1st line chemotherapy with gemcitabine plus cisplatin in the ABC-02 trial,⁹ while the rate of Grade 3 or 4 toxicity was reported as 32% for 2nd line chemotherapy (predominantly 5-fluorouracil-based combinations) in a multicenter, retrospective AGEO analysis.⁶

Re-induction and Second Course safety will also be described at completion of study.

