5.2 Trial Treatments

5.2.1 Dose Selection

The rationale for selection of doses and schedules to be used in this trial is provided in Section 4.0 – Background and Rationale. The treatment to be used in this trial is outlined below in Table 2. See Study Flow Chart (Section 6.0) for additional information on treatment schedule.

Table 2 Trial Treatment

Drug	Dose	Dose Frequency	Route of Administration	Treatment Period ¹	Use
Pembrolizumab	200 mg	Once Q3 weeks	IV infusion over 30 minutes	Every 3 week cycle for up to 24 months or 35 cycles (see Section 5.8)	Experimental
GM-CSF	250 µg	Daily on days 1-14 Q3 weeks for 2 cycles	SC**	Two Induction Cycles: Cycles 2 and 3 in Safety Cohort (n=9) and Expansion Cohort (n=15); Cycles 1 and 2 in Efficacy Cohort	Experimental

Key: IV=intravenous; SC=subcutaneous. ¹A subset of patients may be eligible for Second Course pembrolizumab and/or re-induction with GM-CSF (see Section 7.1.5). *Cycle length is 21 days (Q3 weeks) with GM-CSF “induction” in Cycles 2-3 (Safety and Expansion Cohorts) or 1-2 (Efficacy Cohort). **Patients will be instructed on self-injection administration prior to first dose, with re-training each cycle or more often as needed.

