5.2.2 Dose Modifications or Interruptions for Toxicity

Toxicity will be assessed according to the NCI CTCAE v4.0. Dose modifications, interruptions, and treatment discontinuation for one or both study drugs will be determined according to the system showing the greatest degree of toxicity and according to the treating investigator's assessment of toxicity attribution. Toxicity will be formally assessed at protocol-defined safety assessment time points well as by investigator review of weekly laboratory testing and, in the interim, by patient contact with the study team. General principles of toxicity management are listed below:

- Laboratory values should be rounded to one significant digit for grade determination according to standard rounding practice.
- Optimal supportive care should be provided for all clinically relevant toxicity.
 - See section 5.6 for guidance on supportive care/rescue medications for specific toxicities.
- Dose interruptions or delays in start of a cycle for any reason (toxicity or non-toxicity) during the Induction Phase (Cycles 1 and 2 in Efficacy Cohort, Cycles 2 and 3 in Safety and Expansion Cohorts) should be applied to both drugs together so that both drugs are restarted on Day 1 of each cycle.

- Doses of GM-CSF which are held during a cycle due to toxicity will not be re-administered.
- Doses of GM-CSF which are missed/skipped (e.g. due to logistical reasons, patient oversight, or other non-toxicity related factors) may be made up at end of cycle, daily for up to 3 doses. Missed/skipped doses >3 will not be re-administered.
- A patient will be removed from protocol therapy if pembrolizumab is permanently discontinued but may continue on pembrolizumab if GM-CSF is discontinued for toxicity before completing induction (2 cycles).
- For any toxicity (regardless of grade), despite optimal supportive care, that is felt by the treating investigator to represent a risk to the patient's safety, additional dose reduction, treatment delay, or treatment discontinuation is permitted at the discretion of the treating investigator.

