 - Initiate systemic corticosteroids at a dose of 1 to 2 mg/kg/day prednisone or equivalent for severe immune-mediated adverse reactions.
 - Administer corticosteroid eye drops to patients who develop uveitis, iritis, or episcleritis. Permanently discontinue ipilimumab for immune-mediated ocular disease that is unresponsive to local immunosuppressive therapy.
- **Infusion reactions:** Signs and symptoms usually develop during or shortly after drug infusion and generally resolve completely within 24 hours of completion of infusion.

Table 4 below shows treatment guidelines for subjects who experience an infusion reaction associated with administration of pembrolizumab (MK-3475).

Table 4 Infusion Reaction Treatment Guidelines

NCI CTCAE Grade	Treatment	Premedication at subsequent dosing
Grade 1 Mild reaction; infusion interruption not indicated; intervention not indicated	Increase monitoring of vital signs as medically indicated until the subject is deemed medically stable in the opinion of the investigator.	None
Grade 2 Requires infusion interruption but responds promptly to symptomatic treatment (e.g., antihistamines, NSAIDS, narcotics, IV fluids); prophylactic medications indicated for <=24 hrs	Stop Infusion and monitor symptoms. Additional appropriate medical therapy may include but is not limited to: IV fluids Antihistamines NSAIDS Acetaminophen Narcotics	Subject may be premedicated 1.5h (\pm 30 minutes) prior to infusion of pembrolizumab (MK-3475) with: Diphenhydramine 50 mg po (or equivalent dose of antihistamine). Acetaminophen 500-1000 mg po (or equivalent dose of antipyretic).

NCI CTCAE Grade	Treatment	Premedication at subsequent dosing
	
Increase monitoring of vital signs as medically indicated until the subject is deemed medically stable in the opinion of the investigator. If symptoms resolve within one hour of stopping drug infusion, the infusion may be restarted at 50% of the original infusion rate (e.g., from 100 mL/hr to 50 mL/hr). Otherwise dosing will be held until symptoms resolve and the subject should be premedicated for the next scheduled dose.
 
Subjects who develop Grade 2 toxicity despite adequate premedication should be permanently discontinued from further trial treatment administration.
	

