Grades 3 or 4	
Stop Infusion.
 
Additional appropriate medical therapy may include but is not limited to:
 
IV fluids Antihistamines NSAIDS Acetaminophen Narcotics Oxygen Pressors Corticosteroids Epinephrine
 
Increase monitoring of vital signs as medically indicated until the subject is deemed medically stable in the opinion of the investigator. Hospitalization may be indicated.
 
Subject is permanently discontinued from further trial treatment administration.
	No subsequent dosing

Appropriate resuscitation equipment should be available in the room and a physician readily available during the period of drug administration.

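### The safety population requires a dose of both drugs, so an Expansion Cohort patient stopped for toxicity in the pembrolizumab-only first cycle drops out of the final safety rate

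*Combined protocol and SAP*

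**What the plan says.** SAP Section 8.5.1 defines the safety population as "all enrolled patients who receive at least one dose each of pembrolizumab plus GM-CSF and have the potential to complete 3 cycles". Its next sentence starts evaluability at first treatment with the combination, not at the first dose of either drug. Section 8.3.2 (item 1) likewise describes the safety assessment in terms of subjects who have received both pembrolizumab and GM-CSF induction.

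The Expansion Cohort follows the Safety Cohort schedule, "starting with 1 cycle of pembrolizumab monotherapy before adding induction GM-CSF during Cycles 2 and 3" (Section 4.3.5.1; also Table 2 in Section 5.2.1). The Efficacy Cohort starts both drugs on Day 1 of Cycle 1.

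On stopping, Section 5.2.2 states: "A patient will be removed from protocol therapy if pembrolizumab is permanently discontinued". For infusion reactions, Section 5.6.1 says "Signs and symptoms usually develop during or shortly after drug infusion", and for Grades 3 or 4: "Subject is permanently discontinued from further trial treatment administration".

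The safety hypothesis in Section 3.2 concerns related Grade 3 or higher toxicity over the first three cycles, with a limit of 50%. For the pembrolizumab-first schedule, Section 8.4.4 spells that window out as "1 cycle single-agent pembrolizumab followed by 2 induction cycles with GM-CSF for total of 9 weeks".

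Section 8.6.2.1, which describes the safety tables, uses all subjects as the denominator without defining them or citing Section 8.5.1.

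**The concern.** Taken together, these rules make entry to the safety population depend on surviving Cycle 1 without a treatment-ending toxicity. A severe reaction at the first pembrolizumab infusion is a concrete route: permanent discontinuation, removal from protocol therapy, no GM-CSF, and hence no place in the safety population. If that reaction is treatment-related, it is the kind of event the Grade 3 or higher rate is meant to count, and it falls in a cycle that the rate is meant to cover.

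When such an event patient is dropped, the reported rate is biased low. Safety of this novel combination is a key secondary endpoint (Section 4.3.6.3), so the denominator should not be selected on the outcome. The start-of-evaluability sentence adds a second ambiguity: read literally, it leaves it unclear whether Cycle 1 events count even for Expansion patients who do go on to GM-CSF.

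**Working it through.** **Who is exposed.** The cohorts are 9 (Safety), 18 (Efficacy) and 15 (Expansion), and 9 + 18 + 15 = 42, as planned. Pembrolizumab-first patients number 9 + 15 = 24 (24/42 = 57%). The Safety Cohort is complete. Its reported interim rate of 11%, with one related SAE, reproduces as 1/9 = 11.1%; a denominator of 8 would give 12.5%. All nine therefore appear to have been counted. The Efficacy Cohort starts both drugs together. That leaves mainly the Expansion Cohort, 15/42 = 36%. This is the share on the schedule, not the share likely to be excluded.

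**How many might be lost.** The documents give no Cycle 1 stop rate, so assumptions are needed:
- related Grade 3 or higher rate over three cycles: 1/9, from the interim;
- share of those events in Cycle 1: one third (assumed even spread);
- share of Cycle 1 events that lead to a permanent stop before GM-CSF: f = 0.25, 0.5 or 1.0 (assumed).

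Expected event patients in the Expansion Cohort: 15 × 1/9 = 1.67. In Cycle 1: 1.67/3 = 0.56. The per-patient probability of loss is p = (1/9)(1/3)f, the expected loss is 15p, and the number lost is Binomial(15, p).

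| f | p | Expected loss | None lost | Exactly one | Two or more |
|---|---|---|---|---|---|
| 0.25 | 0.0093 | 0.14 | 87.0% | 12.2% | 0.8% |
| 0.5 | 0.0185 | 0.28 | 75.5% | 21.4% | 3.1% |
| 1.0 | 0.0370 | 0.56 | 56.8% | 32.8% | 10.5% |

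Without the interim rate, one can instead assume that 2%, 5% or 10% of patients stop for toxicity in Cycle 1. The chance of at least one among 15 is then 1 − (1 − q)^15 = 26%, 54% or 79%.

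**Effect on the rate.** With x events among N treated patients and k event patients excluded, the reported rate is (x − k)/(N − k) instead of x/N. The event counts below are assumed; intervals are Clopper-Pearson 95%.

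| Group | All treated | One event patient excluded | One event-free patient excluded |
|---|---|---|---|
| Expansion | 2/15 = 13.3% (1.7–40.5) | 1/14 = 7.1% (0.2–33.9) | 2/14 = 14.3% (1.8–42.8) |
| All cohorts | 5/42 = 11.9% (4.0–25.6) | 4/41 = 9.8% (2.7–23.1) | 5/41 = 12.2% (4.1–26.2) |

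The bias is downward when the excluded patient had a counted event, and slightly upward otherwise.

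**The 50% limit.** To bring an overall rate from above the limit down to it would take, for example, 22/42 = 52.4% with two event patients excluded: 20/40 = 50.0%. One exclusion gives 21/41 = 51.2%, still above. With an interim rate of 11%, this is remote.

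**The case against.** The strongest reply is that Section 8.6.2.1 uses all subjects as its denominator, and on its plain words a treated patient who stops in Cycle 1 is a subject. That wording is undefined, however, and cannot be taken to override an explicit population definition and an endpoint description that both require the two drugs. What stands is that the plan contains two possible denominators, which is itself a reason to fix the text.

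A second reply is that the replacement clause in Section 8.5.1 gives as examples withdrawn consent and biliary complications unrelated to treatment toxicity, which suggests that toxicity dropouts were meant to stay in. That is a fair reading of intent, but the entry rule then defeats the intent.

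Third, the both-drugs rule could be deliberate, since the objective is safety of the combination. That justifies a supplementary both-drugs table. It does not justify the main population when the stated window includes the single-agent cycle.

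Fourth, the interim wording, under which patients could have completed three cycles "or been removed for related toxicity events showed acceptable safety to continue enrollment", is at least partly a trigger for when the analysis could be done. It does not prove that a patient removed before GM-CSF would have been counted, and I rely on it only as a sign that early toxicity removals were expected to matter.

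Finally, the size rests on 1/9, whose exact 95% interval is about 0.3% to 48%, and on assumed fractions. The f = 1.0 row is an upper bound, because Table 3 holds and restarts treatment for several Grade 3 events. Nor are events lost from the database: AEs are recorded from consent (Section 7.2), and Grade 3–5 events are reviewed monthly (Appendix 11.1). These points limit the consequence but do not remove the defect.

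**Conclusion.** The concern holds. As written, Sections 8.5.1 and 8.3.2 exclude an Expansion Cohort patient who stops permanently for toxicity before GM-CSF, and that exclusion depends on the outcome being reported. Confidence is high for the reading of the text and much lower for any particular number.

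The likely effect is zero or one patient: under the stated assumptions, no loss in 57% to 87% of trials. One lost event patient lowers an assumed overall rate by about 2 points (11.9% to 9.8%) and an assumed Expansion Cohort rate by about 6 points (13.3% to 7.1%), in both cases well inside the confidence intervals. Only the final descriptive safety rate is affected. The primary ORR analysis, the completed interim analysis and safety oversight are not. It should be fixed because the plan contradicts its own window and the remedy costs almost nothing, not because the number is likely to move far.

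**What to change.** - In Section 8.5.1, define the safety population as all patients who receive at least one dose of either study drug.
- State that adverse events count from the first dose of either drug. This confirms the Cycle 1 Day 1 start already implied by Sections 3.2, 4.3.6.3 and 8.4.4.
- Say that treated patients remain in the safety tables even if they are replaced for evaluability; otherwise the replacement clause could remove treated patients by another route.
- Align Section 8.3.2 with this population, and name it as the denominator in Section 8.6.2.1.
- If toxicity under combined exposure is of separate interest, keep the both-drugs subset as a supplementary table.

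The cost is SAP wording and at most one extra table. No new data are needed, and no dose or clinical rule changes. The reported rate may come out slightly higher.
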